All participants will complete a breath alcohol test on arrival. Urine drug and pregnancy testing will then be conducted for all participants to test for evidence of recent illicit drug use (e.g. cannabis, cocaine, opioids) and pregnancy. Participants with a positive BAL or urine drug screen positive for any drug except THC will be sent home and the session re-scheduled. Participants who have a 2nd positive BAL, 2nd positive urine drug screen or confirmed positive pregnancy test will be immediately discharged from the study. The Time Line Follow Back (TLFB) procedure will be conducted to record substance use since the last study visit (intake assessment or prior experimental session). Concomitant medications, including vitamins and herbal supplements taken within 14 days prior to the first experimental session and throughout study participation will be recorded. Changes in medication occurring between the screening assessment and first experimental session, or between subsequent experimental sessions will be reviewed by a study investigator and medical staff prior to starting the session to ensure the volunteer is still eligible to participate.

Baseline Assessments. Prior to drug administration, the following baseline assessments will be completed: 5mL serum blood sample, vital signs (HR, BP), subjective drug effect questionnaire, and a brief cognitive performance battery (see below for details).

Experimental Drug Exposure.

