- 2) Subjective drug effect ratings on computerized questionnaires and vital signs assessments at 0 min, 30 min, 60 min, 90 min, 120 min, 180 min, 240 min, 300 min, and 360 min.
- 3) Subjective ratings of mood at 0, 30 min, 60 min, 90 min, 120 min, 180 min, 240 min, 300 min, and 360 min.
- 4) Cognitive performance tests at 0, 30 min, 60 min, 90 min, 120 min, 180 min, 240 min, 300 min, and 360 min.

Use of medication or tobacco products will not be allowed during the study sessions. Study participants who regularly use tobacco products will be provided a nicotine patch upon request.

Outpatient Discharge. Participants will be discharged after completing final assessments (approximately 6 hours post-exposure). In prior studies conducted in our laboratory, this timeline has been adequate for healthy adults to resolve any effects from acute doses of cannabis that are similar to those used in the present protocol. If a study participant indicates the desire to be discharged from the study early, BPRU medical staff will review the self-reported rating of “drug effect” on the most recent subjective drug effect assessment, performance on the cognitive test battery, and conduct a brief interview with the participant prior to discharge. At the end of each session, study staff will compare vital signs and cognitive performance assessments with baseline data and engage in face-to-face conversation with the participant to ensure that they are fit to leave the unit. Cognitive performance tasks obtained measure psychomotor ability, working memory, higher-order cognitive functioning and attention. If the participant is able to cognitively engage with staff, vital signs are within normative range (HR < 100bpm, SYS BP < 150mmHg, DIA BP < 90mmHg), and performance is not below 20% of baseline, the participant will be cleared to leave without further evaluation. If any of these parameters are not met, medical staff will assess the participant and a formal field sobriety test will be conducted. Note, that multiple members of the BPRU cannabis lab have received formal training on administering field sobriety tests by a Maryland State Police Drug Recognition Expert (DRE). If the participant reports a drug effect or exhibits behavior indicative of impairment/intoxication, the participant will be asked to remain at the BPRU until the drug effect subsides and they can pass a field sobriety test. If vital signs are out of range, then medical staff will evaluate and

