make a determination with regards to whether it is safe for participant to be discharged or remain under observation. Participants will not be allowed to drive home; instructions will be provided at the screening session regarding the need to make alternative transportation arrangements. If a participant fails to arrange a ride, taxi transportation home will be coordinated by study staff and provided free of charge.

For ease of scheduling, we will target conduct of sessions on a weekly basis. Because there are 9 total sessions (with option for 10), some participants may want to complete at an accelerated rate. A minimum of 48 hours will separate each study session and no more than 2 sessions will be completed in a calendar week. These timing parameters will allow for adequate elimination of study drugs between sessions and keeps the frequency of exposure to acceptable levels given that the study population will be infrequent cannabis users at the time of study participation.

Study Measures. A battery of measures will be used to assess participant characteristics and drug effects during the study.

Screening. Initial study screening will be completed over the telephone. During the phone screening assessment, staff will conduct assessments to collect background demographic data (age, gender, self-reported race and ethnicity, height, and weight) and to determine study eligibility (e.g. Medical History Interview, Drug-History Questionnaire, Time Line Follow Back (TLFB) assessment of all substance use for the prior 90 days, self-report of adverse effects following cannabis use). If the volunteer appears eligible based on this interview, a physical examination will be scheduled to be completed at the BPRU by medical staff. All major organ systems, including head, eyes, ears, nose, and throat (HEENT); cardiovascular system; lungs; abdomen (liver/spleen); extremities; skin; central nervous system (CNS); musculoskeletal system, and general appearance will be assessed. Biological specimens will be collected and tested for routine clinical chemistry, hematology, serology, serum pregnancy test (females only), and for evidence of recent illicit drug use.

Experimental Sessions. Vital signs (heart rate, systolic blood pressure (SBP), diastolic blood pressure (DBP)) will be measured in the seated position using an automated monitor.

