Six milliliters of blood will be collected by venipuncture or IV catheter insertion at baseline and again at the 0, 15, 60, 120, and 180-minute post-inhalation time points into vacutainer tubes. Blood will be spun to separate plasma, which will be labeled and stored frozen at -80 °C until shipped frozen on dry ice to a designated laboratory for analysis. The maximum amount of blood to be collected is 36 mL per session, and 324 mL over the course of the entire study (those who complete the optional 10th session will have 360 mL of blood collected total), which is less than the amount typically collected during a single routine blood donation (473ml). Quantitative levels of THC and its metabolites (e.g. 11-OH-THC and THCCOOH) will be obtained. Additional analytical testing (e.g. markers of limonene or stress) may be conducted as deemed appropriate to the current study.

A 22-item Drug Effect Questionnaire will be used to obtain subjective ratings of intoxication. Individual items include ratings of drug effects (i.e. drug effect, pleasant drug effect, unpleasant drug effect) and behavioral/mood states often associated with cannabis intoxication (i.e. relaxed, paranoid, hungry/have munchies). Participants will rate each item using a 100mm visual analog scale (VAS) anchored with "not at all" on one end and "extremely" on the other.

The 20-item State subscale of the State-Trait Anxiety Inventory (STAI) will be used to assess indexes of state anxiety/distress (e.g., current subjective feelings of apprehension, tension, nervousness, worry) before and after drug administration.

A brief battery of cognitive performance assessments will be conducted on aspects of functioning known to be sensitive to the acute effects of THC and cannabis, and which are relevant to functioning in the workplace and/or in operating a motor vehicle. All participants will be trained on the performance tasks to a stable baseline level during the screening session. Tasks include the Digit Symbol Substitution Task (DSST): Participants must hand type patterns presented to them on a computer screen for 90 seconds and outcomes include accuracy and total number of patterns completed in the allotted time; and a

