computerized Paced Serial Addition Task (PSAT): Participants are provided a string of single digit numbers on the computer and must add the total of the prior to integers presented and respond by selecting the answer using the computer mouse on the screen, primary outcome is a summed score of the number of correct trials during the task. Recent studies in our laboratory have shown that these 2 tasks are sensitive to cannabis dose effects.

b. Study duration and number of study visits required of research participants.

Ten study visits will be required (11 for those who complete the additional 10th study session). One visit for screening evaluation, and 9 (with option for 10) outpatient experimental sessions lasting approximately 7 hours each. Because there are so many experimental testing sessions in this trial, and interpretation of data is contingent on a complete data set, participants may be invited to repeat a study session should circumstances arise that result in the loss of data during a session (e.g., failure to obtain blood specimens or missing cognitive testing time points), or protocol deviation that impacts data integrity. This is not expected to occur for most participants. Because the study involves repeated collection of blood samples, participants may not repeat more than 4 testing sessions (only 3 sessions may be repeated if they also completed the 10th session), as this would result in cumulative blood collection that would exceed what is typically collected during a single routine blood donation (473mL); see Risks, section 7, below. That said, it would be very unlikely for a participant to repeat more than 1 test session.

c. Blinding, including justification for blinding or not blinding the trial, if applicable.

THC/terpenoid dose assignment will be double-blinded in this study. That is standard procedure for appropriate scientific control in studies evaluating the dose effects of psychoactive drugs.

d. Justification of why participants will not receive routine care or will have current therapy stopped.

e.

Participants in this study will be healthy volunteers. Routine care for any medical illness that may arise during participation will not be affected.

f. Justification for inclusion of a placebo or non-treatment group.

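### The cognitive criterion for discharge, as worded, is met after a loss of up to 80% of baseline performance; a limit of 20% below baseline was probably meant

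*Protocol*

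**What the plan says.** The discharge rule is in the protocol, section 4 (Study Procedures), under Outpatient Discharge. At the end of each session, staff compare vital signs and cognitive scores with baseline and "engage in face-to-face conversation with the participant to ensure that they are fit to leave the unit". A participant is released if three conditions hold together: ability to engage cognitively with staff; heart rate below 100 bpm, systolic pressure below 150 mmHg and diastolic pressure below 90 mmHg; and the performance condition, "performance is not below 20% of baseline, the participant will be cleared to leave without further evaluation".

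The consequence of failing is also stated: "If any of these parameters are not met, medical staff will assess the participant and a formal field sobriety test will be conducted". A separate rule covers reported or observed effects: "If the participant reports a drug effect or exhibits behavior indicative of impairment/intoxication, the participant will be asked to remain at the BPRU", until the effect subsides and a field sobriety test is passed. The section adds: "Participants will not be allowed to drive home".

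Under Study Measures, Experimental Sessions, the protocol explains the choice of tasks. They cover functions described as "relevant to functioning in the workplace and/or in operating a motor vehicle", and earlier work in the laboratory is said to show that "these 2 tasks are sensitive to cannabis dose effects". The Baseline Assessments paragraph places the cognitive battery before dosing: "Prior to drug administration, the following baseline assessments will be completed".

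**The concern.** The clause appears to confuse *20% of baseline* with *20% below baseline*. As worded, it sets the pass mark at one fifth of the participant's own unimpaired score. Tasks chosen because they respond to THC, and used here to judge fitness to leave, would then raise an alarm only after a near-total collapse in performance.

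What is at stake is participant safety at the end of the session. Failing the performance condition is one of the triggers for a medical assessment and a field sobriety test. Under the literal text, someone who has lost, say, half of baseline performance does not set off that trigger. The performance test is the objective cognitive check in the rule; engagement with staff, reported drug effect and visible impairment rest on self-report or observation. Its particular value is in detecting the participant who seems well but is not, and the wording largely removes that value. The rule is applied after each of 9 or 10 sessions per participant.

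**Working it through.** **Inputs**
- Cut-off as written: 20% of baseline (Outpatient Discharge).
- Direction of scoring, from Study Measures, Experimental Sessions: the DSST yields accuracy and the number of patterns completed, and the PSAT yields the number of correct trials. Higher is better on all of these.
- Baseline scores: none are given in the protocol. The DSST baselines of 40, 50 and 60 used below are assumptions for illustration only.

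**The rule as written.** Let B be the baseline score and S the score at discharge. The condition is met if S ≥ 0.20 × B. The largest loss that still passes is 1 − 0.20 = 0.80, or 80% of baseline.

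**The likely intended rule.** Not more than 20% below baseline means S ≥ (1 − 0.20) × B = 0.80 × B. The largest loss that still passes is 20%.

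**Difference between the readings**
- Ratio of the pass marks: 0.80 / 0.20 = 4, whatever the baseline.
- Width of the band in which they disagree: 0.80 − 0.20 = 0.60 of baseline, from 20% to just under 80%.

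| Assumed baseline B | Pass mark as written (0.20 × B) | Likely intended pass mark (0.80 × B) | Whole scores that pass the first and fail the second |
|---|---|---|---|
| 40 | 8 | 32 | 8–31 (24 scores) |
| 50 | 10 | 40 | 10–39 (30 scores) |
| 60 | 12 | 48 | 12–47 (36 scores) |

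The table only puts the two cut-offs in units of the task. It says nothing about how often a participant would fall in the disputed band, because the protocol gives no distribution of scores at 360 minutes.

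**Is the literal cut-off a deliberate choice?** The stated purpose of the comparison is to establish fitness to leave, and the tasks are described as sensitive to cannabis dose. The vital-sign limits in the same sentence are called a normative range. A performance limit that tolerates an 80% loss fits neither that purpose nor those neighbouring limits. The cut-off is stated only once, so nothing elsewhere confirms or corrects it.

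**The case against.** The strongest reply is that this is loose wording, not a decision anyone made. The purpose is stated just before the clause, and trained staff would probably read it as a 20% decrement. Nothing suggests that the team would apply a cut-off at one fifth of baseline.

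The other safeguards also cover most of the consequence. Subjective drug-effect ratings are collected at 360 minutes, so a persisting effect is elicited systematically just before discharge, and a participant who reports one is held. Discharge comes about 6 hours after exposure, an interval the protocol says has been adequate for similar doses. Driving home is barred and a free taxi is available, which weakens any argument from the tasks' relevance to driving. Harm would need a participant who has lost substantial performance yet reports no effect, converses normally, shows no impairment and has normal vital signs.

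Finally, the proposed text goes further than the error requires. The rule says only baseline and performance, training at screening also aims at a stable baseline level, and requiring a pass on both tasks is a choice.

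Most of this stands as a limit on the consequence. It does not rescue the wording: an operational safety rule that staff must read against its own words is badly fixed, and the safeguards do not replace an objective performance check. The experience with similar doses is reassuring, but the earlier vaporized study in this laboratory used 10 and 25 mg of THC, against a top dose of 30 mg here. On the remedy, the pre-dose battery is what the Baseline Assessments paragraph defines as baseline, and the DSST and PSAT are the only cognitive tasks named. The added detail therefore follows the protocol, although correcting the error itself needs only the change of cut-off.

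**Conclusion.** The concern holds. The performance condition is wrong as written: it passes any score down to 20% of baseline, a loss of up to 80%, where a limit of 80% of baseline was probably meant. The literal reading rests only on the wording and on both tasks being scored higher-is-better, and it is firm. The intended value is an inference from the stated purpose of the check; the protocol does not give it.

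The practical gap is limited to a participant who satisfies every other check but still performs poorly. How often that would happen is unknown. No endpoint, estimate or analysis is affected. The correction should be made because the clause governs participant safety and costs almost nothing to put right.

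**What to change.** In section 4, Outpatient Discharge, replace the performance condition with: *performance is not more than 20% below that session's pre-dose baseline (at least 80% of the baseline score) on the DSST and the PSAT*. The clinical team should confirm that 20% is the value it wants. Because the DSST yields both accuracy and number completed, it would help to name the score that counts.

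No new data are needed, since the battery is already given before dosing and at 360 minutes. The cost is one clause in the protocol and possibly a few more medical assessments and field sobriety tests at the end of sessions.
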